### **5.7.3 Vital Signs**

Vital sign data will present measurements for height, weight, BMI, systolic and diastolic blood pressure, pulse rate, respiratory rate, pulse oximetry and temperature. Vital signs (absolute values and change from baseline) will be summarized (n, mean, SD, median, minimum and maximum) and listed per visit, per treatment group and overall, using protocol visits. Mean (SD) of absolute values for vital signs data (blood pressure, pulse rate and respiratory rate) will also be presented graphically through time.

If applicable, vital sign measurements collected as additional/unscheduled assessments (i.e. apart from those per protocol) will only be listed and will not be used in summary statistics or graphical presentations.

### **5.7.4 ECG**

From the 12-lead ECG data, HR, PR interval, QRS interval, QT interval, RR interval and QTcF will be reported for each visit and summarized using descriptive statistics. Change from baseline will be calculated as well, using the same summary statistics. Mean (SD) temporal profiles for 12-lead ECG (QT, QTcF) will be presented graphically. Clinically significant findings will only be listed.

If applicable, ECG measurements collected as additional/unscheduled assessments (i.e. apart from those per protocol) will only be listed and will not be used in summary statistics.

### **5.7.5 Prior and concomitant medication**

The use of concomitant medication will be listed for all patients: included will be the medication generic name, WHO coding information, dose, route of administration, start and stop date, frequency and reason for administration, as well as information if given for an AE. Differentiation will be made between prior and concomitant medication, by creating two separate listings.

Separate frequency tables will be presented for prior and concomitant medication per Standardized Medication Name as provided.

If a medication is started and stopped prior to the first dosed of study medication, then it is considered prior medication. In other instances, it is considered concomitant. In case of (partially) missing start/stop dates, refer to Section 5.2.

### **5.7.6 Physical examination**

All abnormalities reported by the physical examinations will be listed.

### **5.7.7 Nerve conduction study (NCS)**

NCS consists of the following assessments: Hand Temperature (°C), Foot Temperature (°C), SRAR, SNAP (µV) and SCV (m/s). The latter two have been determined for locations Median Nerve, Ulnar Nerve, Radial Nerve, Sural Nerve. Descriptive statistics will be presented for all assessments, irrespective of being performed per NCS protocol or quality assessment result. The following descriptive displays will be presented:

- Descriptive statistics per visit and treatment arm, including change from baseline.
- Mean +/- SD plots versus time
- Shift from baseline categories (presenting frequencies and percentages per visit and treatment arm)
- Percentage drop >50% from baseline (presenting frequencies and percentages per visit and treatment arm)
- Normal/abnormal classification results (presenting frequencies and percentages per visit and treatment arm)

Information on high/low/normal categorization is presented in section 9.1.

In case of multiple measurements for a specific visit, repeats have occurred because of a measurement being not quality approved. In those instances, the last repeated value will be used for the descriptive statistics. All collected values will be listed.

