**8.2.5. Nerve Conduction Study**

The NCS protocol evaluates the sensory nerve action potential (SNAP) amplitudes using standard ring-electrodes and predefined sites for both stimulus (antidromic) and recording sites, including standardized distances that also apply for the inter-electrode distances. Hence, routine signal averaging for the recorded SNAP's will be performed after supramaximal stimulation. These measures will eliminate any unwanted variation due to instrumental differences. For these recordings, limb temperature should be at 31°C, otherwise warming may be considered or alternatively accepted correction factor for decreased temperature could be done. Sensory latencies and velocities are less robust parameters that may also depend on filter settings between different machines and, therefore, will not be used. NCS criteria for neuropathy are decreased sural nerve SNAP amplitudes or decreased sural/radial nerve amplitude ratio (SRAR).

NCS will include sensory recordings from sural nerves (unilateral) and sensory recordings from median, ulnar, radial nerves (unilateral) with standardized distances between recording and stimulation sites of 12cm. NCS data will be evaluated by neurophysiologists at the participating centres and also reviewed independently at the UMC Utrecht, taking into account reference values provided by participating sites, and using age adjusted reference values. Additional testing may be requested if required.

Instructions on operational aspects of the NCS are described in a separate NCS manual.

The main aim of NCS is to identify subclinical damage of sensory function before the potential development of a clinically significant neuropathy. The relevant expected clinical presentation of neuropathy is predominantly sensory and includes relative symmetric paraesthesia and/or numbness mainly in feet.

The DSMB will assess the results of the NCS, simultaneously with the assessment on vitamin B6, clinical signs, ALSFRS-R questions related to leg functioning (8. walking and 9. climbing stairs) for the first enrolled 60 patients (about 40 active and 20 placebo).

The NCS will be conducted for the first enrolled 60 patients at screening, and on weeks 4, 12, and 24. Then according to the evaluation by the DSMB, one of the following options will be performed:

---

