## Nerve conduction study (NCS)

Normal ranges for NCS are defined as below. Values below the lower limit are considered LOW, values above the upper limit HIGH, and otherwise (if not missing) values are considered to be NORMAL.

Parameter	Age group	Lower limit	Upper limit
Hand Temperature (°C)	-	30	37
Foot Temperature (°C)	-	30	37
Median Nerve – SNAP Amp (µV)	< 60 yrs	11	-
	> 60 yrs	5	-
Median Nerve – SCV (m/s)	-	30	70
Ulnar Nerve – SNAP Amp (µV)	< 40 yrs	11	-
	40 - ≤ 60 yrs	7	-
	> 60 yrs	5	-
Ulnar Nerve – SCV (m/s)	-	30	70
Radial Nerve – SNAP Amp (µV)	< 40 yrs	11	-
	40 - ≤ 60 yrs	7	-
	> 60 yrs	5	-
Radial Nerve – SCV (m/s)	-	30	70
Sural Nerve – SNAP Amp (µV)	< 40 yrs	8	-
	40 - ≤ 60 yrs	5	-
	> 60 yrs	2	-

Sural Nerve – SCV (m/s)	-	30	70
Sural-Radial Amp Ratio (SRAR)	< 40 yrs	0.45	-
	40 - $\leq$ 60 yrs	0.32	-
	> 60 yrs	0.19	-

Percentage change from baseline will be calculated as (value – baseline)/baseline.

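### The SAP's limits for median-nerve sensory amplitude omit age 60 and default to normal, and no nerve conduction summary is restricted to quality-approved recordings

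*SAP*

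**What the plan says.** **Which recordings are tabulated.** SAP section 5.7.7 states: "Descriptive statistics will be presented for all assessments, irrespective of being performed per NCS protocol or quality assessment result". This introduces all the nerve conduction study (NCS) displays: statistics by visit with change from baseline, mean plots, shift tables, drops of more than 50%, and normal/abnormal counts. For several measurements at one visit, the section explains that "repeats have occurred because of a measurement being not quality approved" and that "the last repeated value will be used for the descriptive statistics". It adds: "All collected values will be listed". Neither this section nor the table list in SAP 10.3 names a summary limited to approved recordings.

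**How values are classified.** The NCS table in SAP 9.1 calls a value LOW below the lower limit and HIGH above the upper limit; "otherwise (if not missing) values are considered to be NORMAL". Median SNAP has two age rows, under 60 (11 µV) and over 60 (5 µV). Ulnar, radial and sural SNAP and SRAR have a middle band that runs from 40 up to and including 60. SCV limits have no age band.

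**What the protocol wants from NCS.** Protocol 8.2.5 standardises the technique, adds independent central review, and gives the aim as finding subclinical sensory damage early. Its NCS criteria for neuropathy are a reduced sural SNAP or a reduced SRAR.

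**The concern.** NCS is the trial's dedicated neurotoxicity monitor. Protocol 2.2 ties it to neurological findings in animals at relatively low safety margins, and Protocol 9.1.4 makes significant NCS abnormalities adverse events of special interest.

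Two rules make the planned tables less reliable than they could be at no extra data cost. First, a gap in an age band combined with a default produces a definite class, NORMAL, where no limit exists. A blank would at least be visible; a wrong class is not. Second, the trial obtains a quality verdict on each recording, but the tables use it only indirectly, through the repeat rule. A reader of the study report could not tell how far a table rests on recordings that failed review.

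**Working it through.** The plan gives no figure of its own to reproduce. The first check applies the SAP 9.1 limits literally; the second follows a recording through SAP 5.7.7.

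**1. Lower limits around age 60 (SAP 9.1)**

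| Parameter | Age 59 | Age 60 | Age 61 |
|---|---|---|---|
| Median SNAP (µV) | 11 | none | 5 |
| Ulnar SNAP (µV) | 7 | 7 | 5 |
| Radial SNAP (µV) | 7 | 7 | 5 |
| Sural SNAP (µV) | 5 | 5 | 2 |
| SRAR | 0.32 | 0.32 | 0.19 |
| SCV, each nerve (m/s) | 30 to 70 | 30 to 70 | 30 to 70 |

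Only median SNAP is affected. Example amplitudes at age 60:

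| Amplitude (µV) | Literal text | If 60 joins the lower row (limit 11) | If 60 joins the upper row (limit 5) |
|---|---|---|---|
| 1 | NORMAL | LOW | LOW |
| 4 | NORMAL | LOW | LOW |
| 6 | NORMAL | LOW | NORMAL |
| 10 | NORMAL | LOW | NORMAL |
| 12 | NORMAL | NORMAL | NORMAL |

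The gap reaches the normal/abnormal table and the shift table. Mean values, change from baseline and the table of drops above 50% do not use the limits.

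*How many patients.* Ages 18 to 80 are eligible (Protocol 5.2); the number aged 60 is not given. Assuming 1% to 5% of 300: 0.01 × 300 = 3 and 0.05 × 300 = 15 patients (2 to 10 active, 1 to 5 placebo). This treats age as completed years. With decimal age, 60.5 falls in the over-60 row and almost nobody is affected. SAP 9.1 does not say which is used.

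**2. Which failed recordings remain (SAP 5.7.7)**

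- Failed, then repeated and approved: replaced in the tables.
- Failed and never repeated: stays in.
- Failed, and the last repeat also failed: the failed repeat stays in.

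Let *f* be the share of tabulated recordings that are still failures after this rule, *p* the true rate of drops above 50%, and *q* the rate at which a failed recording shows such a drop. The tabulated rate is (1 − f)p + fq. All rates below are assumed, for illustration only.

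- *Equal failure in both arms*, p = 15% active and 5% placebo: the difference becomes (1 − f) × 10 points, that is 9.5 at f = 5%, 9.0 at f = 10% and 8.0 at f = 20%.
- *The rates themselves move either way.* At f = 10% with q = 0%: 0.9 × 15 = 13.5% and 0.9 × 5 = 4.5%, both too low. With q = 30%: 13.5 + 3 = 16.5% and 4.5 + 3 = 7.5%, both too high.
- *Unequal failure, no true effect* (p = 5% in both arms, q = 30%): with f = 10% active, 4.5 + 3 = 7.5%; with f = 5% placebo, 4.75 + 1.5 = 6.25%. That is a spurious 1.25 points against active; swapping the arms reverses the sign.

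**The case against.** The strongest reply is that SAP 5.7.7 makes an open choice for descriptive displays with no planned NCS test. Showing all safety data is defensible, because dropping failed recordings could itself be selective. That stands, and it is why an approved-only table should be added rather than replace the all-recordings table.

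Three stronger readings are tempting, and the documents do not support them.

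- *That quality review is ignored altogether.* The last-repeat rule replaces every failed recording that was successfully repeated. SAP 5.2 also lets the blinded data review exclude unambiguous measurement errors, although that is discretionary.
- *That the whole median nerve is classed as normal at 60.* Only SNAP amplitude is; median SCV keeps its limits at every age.
- *That the neurotoxicity signal is weakened.* Sural SNAP and SRAR, the protocol's criteria, are classified at 60. Remaining failures can add false abnormal results as well as hide true ones. Detection does not rest on these tables alone: there is site and central reading with age-adjusted references (Protocol 8.2.5), reporting of events of special interest to the sponsor and the data safety monitoring board (DSMB) (Protocol 9.1.4), and DSMB review of the first 60 patients.

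It can also be said that a programmer would leave a 60-year-old's median SNAP unclassified. That may happen, but the written default says otherwise.

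**Conclusion.** Both gaps are in the text, and both are minor.

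At age 60, the literal SAP 9.1 rule classes every non-missing median SNAP amplitude as NORMAL. On its own this can only remove LOW results, in one parameter outside the protocol's neuropathy criteria. It affects an unstated number of patients: 3 to 15 if 1% to 5% are aged 60 in completed years.

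In SAP 5.7.7, unrepeated failures and failed last repeats stay in every NCS summary, with no approved-only counterpart. The effect can go in either direction. Its size cannot be given, because the documents state no failure rate and do not say how often repeats succeeded. The dilution figures above rest entirely on assumed rates.

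**What to change.** Before database lock:

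1. **Close the median SNAP age band in SAP 9.1.** Writing the lower row as ≤ 60 matches the other age-banded parameters, where 60 falls below the break. The sponsor should confirm whether 11 or 5 µV was intended at 60, and the SAP should say whether age is in completed years. The cost is one symbol and one sentence.
2. **Add approved-only NCS summaries to SAP 5.7.7 and 10.3**: change from baseline, shift, drops above 50% and normal/abnormal, using the last quality-approved value per visit. Keep the all-recordings tables and the full listing. The cost is one filter and a set of extra tables; the drawback is fewer values per visit in the added tables. Reporting the number of non-approved recordings by arm and visit would show how much the two sets can differ.

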#### **Visit 5 Week 36 (Day 252 ±7Days)**

The following procedures will be performed:

- Review ongoing concomitant medications
- Neurological examination
- Vital signs measured with the subject in a supine/semi-supine position (for at least 5 minutes prior), including blood pressure, pulse rate, pulse oximetry and temperature
- Fasting blood samples for routine clinical labs (clinical chemistry, haematology). See table 2 for lab assessments
- Urine samples for urinalysis
- Urine pregnancy test only in women of childbearing potential

- Plasma vitamin B6 levels, and, if necessary, vitamin B6 supplements (pyridoxine (100 mg/day)) will be prescribed.
- ALS evaluation procedures: ALSFRS-R, Slow Vital Capacity (SVC), Hand-Held Dynamometry, King's staging system and MiToS, EQ-5D-5L and VAS.
- Blood sampling for biomarker: neurofilament light (NFL). Creatinine and creatine kinase will be measured in routine biochemistry lab testing.
- Urine collection for biomarkers: urinary extracellular domain of neurotrophin receptor p75 (Urinary P75ECD) and oxidative stress biomarker 8-hydroxyguanosine (8-OHdG)
- Blood sampling for RNA and serum collection for FBR (if consented)
- Nerve Conduction Study (NCS) (if required)
- Adverse Events monitoring
- Cost questionnaire
- Dispensing study medication
- Compliance check

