- If no neurological concerns are observed, the study will continue with one additional NCS at week 48 for the first 60 patients. Then for the next enrolled patients, one NCS will be performed at screening and another one at week 48. Additional NCS(s) could be performed between screening and week 48 if any abnormality is detected by the neurological examination or any suggesting symptoms of neuropathy are reported by the patient.
- If NCS show signs of neurological damage, intensive NCS monitoring will continue for all patients at screening and on weeks 4, 12, 24, 36, 48, 60, and 72.

All NCS values will be recorded by the investigator in the eCRF at the corresponding time points.

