5. The DSMB will assess the results of the NCS for the first enrolled 60 patients (about 40 active and 20 placebo). The NCS will be conducted for the first enrolled 60 patients at screening, and on weeks 4, 12, and 24. Then according to the evaluation by the DSMB, one of the following options will be performed: 1) If no neurological concerns are observed, the study will continue with one additional NCS at week 48 for the first 60 patients. Then for the next enrolled patients, one NCS will be performed at Screening and another one at week 48. Additional NCS(s) could be performed between Screening and week 48 if any abnormality is detected by the neurological examination or any suggesting symptoms of neuropathy are reported by the patient. 2) If NCS show signs of neurological damage, intensive NCS monitoring will continue for all patients at Screening and on weeks 4, 12, 24, 36, 48, 60, and 72.
6. Hematology: hematocrit, hemoglobin, RBC (red blood cell count & parameters), WBC (white blood cell count inclusive differential count), platelet count. Biochemistry: total protein, alkaline phosphatase, AST (aspartate transaminase), ALT (alanine transaminase), GGT (Gamma-glutamyl transpeptidase),

7. Vitamin B6 levels will be monitored and, if necessary, supplementation of vitamin B6 (pyridoxine (100 mg/day)) will be prescribed.
8. Urinalysis: Blood, Glucose, Protein, Specific gravity, Ketone, pH, Nitrite, Leukocytes, Bilirubin, Urobilinogen, Microscopic exam, if abnormal results are noted.
9. Blood sampling for FAB122 PK analysis will be done in ~90 subjects in selected sites. Of those ~30 subjects will participate in a PK profiling sampling schedule and the additional ~60 subjects will participate in a population PK sampling schedule. Sampling schedule for PK profiling: pre-dose and 15 min, 30 min, 1, 1.5, 2, 4 hrs., and 6hrs. after the FAB122 morning dose. The pre-dose sample may be collected within 30 minutes prior to dosing, the samples taken 15 and, 30 min post dosing samples should be taken within ±2 minutes of the scheduled time, the 1 hr. post dosing sample within ±5 minutes, the 2-hour sample within ±10 minutes and the 4 hr. and 6hr. sample within ±20 minutes of the scheduled time. The time of sampling will be accurately recorded. Sampling schedule for population PK: (1) pre-dose (within 1 hour prior to dosing), (2) within 5- and 30-minutes post dosing, (3) 1 hour and (4) 1.5 hour after the second PK sample was taken.

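### SAP 5.7.7 does not separate scheduled from triggered nerve conduction recordings, so on the DSMB's no-concern branch the by-visit displays change patient mix from visit to visit

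*SAP*

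**What the plan says.** SAP 5.7.7 states: "Descriptive statistics will be presented for all assessments, irrespective of being performed per NCS protocol or quality assessment result". It then lists the displays, all by visit and arm: descriptive statistics with change from baseline, "Mean +/- SD plots versus time", shift tables, counts of drops above 50%, and normal/abnormal rates. When a visit holds several measurements, the section takes it that "repeats have occurred because of a measurement being not quality approved" and uses the last one.

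The schedule is in Protocol 8.2.5 and in footnote 5 of the visit table, repeated in SAP 2.5: "The NCS will be conducted for the first enrolled 60 patients at screening, and on weeks 4, 12, and 24" ("about 40 active and 20 placebo"). The DSMB review then leads to one of two branches:

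- **No concern.** The first 60 patients have one more NCS at week 48. Later patients have screening and week 48. In addition: "Additional NCS(s) could be performed between screening and week 48 if any abnormality is detected by the neurological examination or any suggesting symptoms" are reported.
- **Signs of damage.** All patients are recorded at screening and weeks 4, 12, 24, 36, 48, 60 and 72.

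Three other rules bear on this. SAP 5.7.2, 5.7.3 and 5.7.4 say that additional or unscheduled laboratory, vital-sign and ECG measurements are listed but not summarised; 5.7.7 has no such sentence. SAP 5.1 takes the whole analysis population as the denominator for percentages. SAP 5.3 maps an unscheduled assessment that follows a missed visit to the nearest earlier visit at which that assessment was due.

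**The concern.** On the no-concern branch, extra recordings are made because someone suspects neuropathy, which is the outcome that NCS measures. If they share columns and plot points with scheduled recordings, each visit describes a different kind of patient. A dip followed by recovery could then appear in a mean plot with no change in any patient. If FAB122 produces symptoms, more of its patients would enter the middle columns, and the arms would be compared on differently selected patients.

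NCS is the trial's special monitoring for a neurotoxic effect seen in animals at relatively low safety margins (Protocol 2.2), so these displays will be read closely. The last-value rule adds a second route: a triggered recording entered under the same visit as a scheduled one would replace it.

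**Working it through.** **1. The plan's own figure.** Under 2:1 allocation, 60 × 2/3 = 40 and 60 × 1/3 = 20. This matches the stated split of the first cohort.

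**2. Who has a scheduled NCS on the no-concern branch** (300 planned, before dropout, first-60 limit applied):

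| Visit | Scheduled | Share of 300 |
|---|---|---|
| Screening | 300 | 100% |
| Weeks 4, 12, 24 | 60 | 20% |
| Week 36 | 0 | 0% |
| Week 48 | 300 | 100% |

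Any value entered under week 36 on this branch is therefore triggered.

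**3. Means (illustration only).** Assumptions, none of them in the documents: a share q of patients is triggered at each visit, their mean amplitude lies d SD below that of other patients, and there is no time trend and no dropout. With the population mean set to 0, triggered patients have mean −(1 − q)d. Weeks 4 to 24 hold 60 scheduled patients plus 240q triggered, so the plotted mean is −240q(1 − q)d / (60 + 240q). Week 36 holds 300q patients with mean −(1 − q)d. Week 48 holds 300 patients with mean 0.

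| q | n, weeks 4–24 (share triggered) | Mean, weeks 4–24: d = 0.5; 1.0 | n, week 36 | Mean, week 36: d = 0.5; 1.0 |
|---|---|---|---|---|
| 5% | 72 (17%) | −0.08; −0.16 | 15 | −0.475; −0.95 |
| 10% | 84 (29%) | −0.13; −0.26 | 30 | −0.45; −0.90 |
| 20% | 108 (44%) | −0.18; −0.36 | 60 | −0.40; −0.80 |
| 30% | 132 (55%) | −0.19; −0.38 | 90 | −0.35; −0.70 |

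With d = 0 every mean is 0. The mix still changes, but the plot does not move.

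**4. Percentages under SAP 5.1.** Assume 5% of scheduled recordings are abnormal, and 6 to 24 patients are triggered with 40 to 50% abnormal.

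- Weeks 12 and 24: (60 × 0.05 + 6 × 0.4)/300 = 5.4/300 = 1.8%, up to (3 + 24 × 0.5)/300 = 15/300 = 5.0%. Among those recorded: 5.4/66 = 8.2% to 15/84 = 17.9%.
- Week 36: 6 × 0.4/300 = 0.8%, up to 24 × 0.5/300 = 4.0%. Among those recorded: 40 to 50%.
- Week 48: 15/300 = 5.0%.

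On the same kind of data the mean plot can dip at week 36 while the abnormal percentage is lowest there. Patient mix and denominator produce both.

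**The case against.** The case against has real force, and most of it limits the point.

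- **The quoted sentence.** A reader might infer that it expressly admits triggered recordings. It probably does not. Protocol 8.2.5 uses the term for recording technique: "The NCS protocol evaluates the sensory nerve action potential (SNAP) amplitudes using standard ring-electrodes". The point rests on the inclusion of all assessments and on the missing list-only rule.
- **Movement by construction.** A reader might infer that the mean must move. Only the mix must change; the mean moves if triggered patients differ. That is plausible given the trigger, but weakness from ALS itself can prompt a test, and these recordings are sensory.
- **Off-visit recordings.** Under SAP 5.3, an NCS done between visits would not be placed at week 36, where none is due on this branch. Mixing is clear only for recordings entered under a planned visit.
- **Week 36 wording.** Protocol 6.3 marks NCS as conditional at weeks 36, 48, 60 and 72 alike, so that wording alone does not show that triggered tests happen at week 36.
- **Weeks 4 to 24.** The visit lists in Protocol 6.3 give NCS there without a first-60 limit. At 300/10 = 30 patients a month, assuming even recruitment, the 60th patient enters at month 2 and reaches week 24 about 5.5 months later. By then about 7.5 × 30 = 225 are enrolled, 165 of them after the first 60. If those patients were recorded routinely, triggered cases would weigh less.
- **Existing cover.** Change from baseline, shifts and drops above 50% use each patient's own baseline. Significant NCS abnormalities are events of special interest (Protocol 9.1.4) and are tabulated under SAP 5.7.1. All values are listed, and n is shown. None of this reports how many patients were triggered in each arm, or stops selected patients from entering the columns.
- **Hiding symptomatic patients.** Removing triggered recordings from the main tables could understate toxicity. A separate by-arm table of those recordings answers this.

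**Conclusion.** The gap is real and modest. SAP 5.7.7, followed as written on the no-concern branch, gives by-visit columns that are partly selected on suspicion of the outcome, and at week 36 wholly so. Elsewhere the SAP already keeps such measurements apart.

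The documents do not say which branch was taken; on the other, week 36 is scheduled for everyone and the week-36 problem disappears. The size of any shift in means cannot be derived from the documents, and the SD figures above only illustrate the mechanism.

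A reader might also infer that the tables would show 8 to 18% abnormal at weeks 12 and 24, and 40 to 50% at week 36. Those are shares of patients recorded. With the SAP 5.1 denominator the same assumed inputs give 1.8 to 5.0% and 0.8 to 4.0%, so the percentages could mask a signal while the means exaggerate one. These are descriptive safety displays, and no hypothesis test, estimand or error rate is touched.

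**What to change.** In SAP 5.7.7, before unblinding:

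1. Flag each NCS as scheduled, under the branch actually taken, or triggered.
2. Restrict by-visit tables and plots to scheduled recordings, with baseline and change on the same patients in each column.
3. Base NCS percentages on patients with an NCS at that visit.
4. Report triggered recordings in a separate table by arm: patients triggered and patients abnormal.
5. State that a triggered recording does not replace a scheduled one under the last-repeat rule.

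The sponsor should also reconcile the week 4, 12 and 24 visit lists in Protocol 6.3 with the first-60 schedule in Protocol 8.2.5, because the flag cannot be set for later patients until that is settled.

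The cost is SAP wording, one derived flag and one extra table. The by-visit displays would hold fewer recordings. No new patient assessments are needed, although the reason for each extra recording must be identifiable in the data.
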